Study 003: Extension of Study 002, carbidopa-levodopa in neovascular AMD

Study Design: Prospective, open-label, fixed dose

PI: [name], PhD

Protocol Version 1

Date: June 24, 2017

IND Number: 132078

ClinicalTrials.gov identifier: NCT 03197493

Overview of extension study: If a patient completes Study 002 without significant problems, and wishes to continue carbidopa-levodopa therapy, he or she may be enrolled in protocol 003, a 9-month extension. Visits will occur monthly and will have the same monitoring at each visit as in protocol 002. Anti-VEGF injections will be administered according to the standard of care, as in protocol 002, with the same criteria for injections. Measurements and procedures at each visit will be the same as in protocol 002. This will allow evaluation of the safety of carbidopa-levodopa over an entire year of treatment.

Objectives:

1. To determine whether L-DOPA-carbidopa supplementation can improve visual function, within 12 months, in patients with choroidal neovascular AMD (nAMD), by testing best-corrected visual acuity (BCVA).
2. To determine whether L-DOPA-carbidopa supplementation in daily doses, approximating those used in Parkinson's disease, is well tolerated for 12 months in our target group of patients with nAMD in one eye.
3. To determine whether L-DOPA-carbidopa supplementation can improve the anatomic findings on optical coherence tomography (OCT), within a total of 12 months, in the eye of patients with nAMD.
4. To determine whether L-DOPA-carbidopa supplementation can improve the anatomic findings on OCT, within 12 months, in the eye without nAMD.
5. To evaluate the effect of carbidopa-levodopa on anti-VEGF injections.

Inclusion Criteria:

- Completion of Protocol 002: Dose ranging study of carbidopa-levodopa.
- A diagnosis of AMD with choroidal neovascularization (CNV) in one eye.
- Normal or Dry AMD of any grade in the fellow eye.
- Age 50-85 years.
- Willingness to maintain AREDS vitamin Supplements throughout the study or remain off these supplements for the duration of the study, if not taking them prior to the study.
- Written informed consent at visit 1.

Exclusion criteria:

- Any current use of L-DOPA containing medication or dopamine agonist medication, or any planned use of any of these agents, except for study medication, during the study.
- Concurrent use of monoamine oxidase (MAO) inhibitors.

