- Nervous system/Psychiatric: delusions, hallucinations, confusion, agitation, dizziness, sleepiness, abnormal dreams, insomnia, abnormal sensations, headache, depression, abnormal movements, mental difficulties, urge to gamble, increased sexual desire, problems with impulse control.
- Respiratory: shortness of breath, upper respiratory infection.

- Skin: Rash, increased sweating, hair loss, dark sweat.
- Urogenital: urinary tract infection, urinary frequency, dark urine.

Dealing with Adverse Events:

Study Participants will be asked about any adverse events at each visit, and asked to tell the study doctor or study staff right away if they have any side effects, or if they have any other problems with their health or the way they feel during the study, regardless of whether or not they think these problems are related to the study drug. The answers will be recorded in the source documents. For minor and easily tolerated events, the participants will continue in the study, unless they request to be withdrawn from the study. For serious or poorly tolerated events, the patient will be withdrawn from the study. Appropriate medical care will be instituted for any serious adverse events.

Number of subjects: 52 completed

Duration: Up to 9 months of treatment.

Measurements and Activities:

- Written informed consent at Visit 1.
- Ophthalmic history and comprehensive eye examination; including visual acuity, with current refraction, using an EDTRS chart, in each of both eyes separately, and ophthalmoscopic examination, and SD-OCT.
- Repeat assessment of visual acuity using an EDTRS chart, ophthalmoscopic examination, and SD-OCT at monthly visits.
- Subjective Vision Questionnaire at monthly visits.
- Demographics obtained at Baseline in Study 002 or Study 001.

- Medical History, Vital Signs and Physical Examination at Baseline in Study 002 or Study 001.
- ECG, CBC, Chem 20 and HbA₁C at Baseline in Study 002 or Study 001.
- Dispense study medication at monthly visits.
- Pill count at monthly visits
- Non-directed assessment of adverse events at each visit, including classification as to severity, seriousness and body system.
- Concomitant medications at each visit.
- If a patient had the baseline evaluation in Study 001, that will be used as the baseline evaluation for this study. If the patient entered directly into Study 002, that will be used as the baseline evaluation for this study.

Criteria for repeat anti-VEGF injections:

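### Does taking baseline from Study 001 for some patients and Study 002 for others undermine the 12-month change in acuity and OCT?

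*Protocol*

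**What the plan says.** The rule closes the list under *Measurements and Activities* in the Protocol. It has two parts: "If a patient had the baseline evaluation in Study 001, that will be used as the baseline evaluation for this study", and "If the patient entered directly into Study 002, that will be used as the baseline evaluation for this study". Neither part says which measurements it covers.

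Earlier bullets in that list name either study as the source for demographics, history, vital signs, physical examination, ECG and laboratory tests, for example "Medical History, Vital Signs and Physical Examination at Baseline in Study 002 or Study 001". The bullets on acuity and OCT carry no such label. They ask for an eye examination with acuity and SD-OCT, and then "Repeat assessment of visual acuity using an EDTRS chart, ophthalmoscopic examination, and SD-OCT at monthly visits".

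The *Overview* says that a patient who completes Study 002 without significant problems and wants to continue may join: "he or she may be enrolled in protocol 003, a 9-month extension". It adds "This will allow evaluation of the safety of carbidopa-levodopa over an entire year of treatment". The *Objectives* set a 12-month limit for acuity, tolerability and OCT without saying when the 12 months begin. Study 001 is not mentioned in either place.

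**The concern.** The study is open-label and describes no comparison group, so the acuity and OCT objectives (1, 3 and 4) naturally rest on change from baseline. If baseline is an earlier date for some patients than for others, a single average change to the last visit mixes different lengths of follow-up. The mix then depends on how many patients came by each route.

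The Overview appears to sharpen the problem. A direct entrant can reach a year of treatment only by adding Study 002 to the nine-month extension, so a Study 001 baseline seems to lie outside the year that the objectives describe. At stake would be the meaning of a 12-month result, and possibly its size.

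**Working it through.** **1. Reproduce the year.** Inputs: visits 25 to 35 days apart (*Treatments*); the extension opens at Visit 5 and ends at Visit 13 (*Tables 1A and 1B*). Assume that Visits 1 to 4 are monthly Study 002 visits, which the document does not state.

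- Visit 1 to Visit 4: 3 intervals × 30 = 90 days.
- Visit 4 to Visit 13: 9 intervals × 30 = 270 days.
- Visit 1 to Visit 13: 12 intervals × 25, 30 or 35 = 300, 360 or 420 days.

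So 3 + 9 = 12 months is reproduced with the start at Study 002. If Visit 5 instead falls at the end of three Study 002 intervals, the count is 3 + 8 = 11 intervals, or 275, 330 or 385 days.

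**2. Add the Study 001 route.** Let L be the time from the Study 001 baseline to the first Study 002 visit. The document does not give L. On either visit count, Study 001 entrants have a span longer by exactly L. With assumed L = 30, 60 or 90 days, the nominal 360 days become 390, 420 or 450.

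The visit windows alone allow 420 − 300 = 120 days of spread within one route. At L = 30 the two ranges are 330–450 and 300–420 days, which share 330–420.

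**3. Effect on a pooled average.** Let p be the share of Study 001 entrants and d their mean change from the Study 001 baseline to the first Study 002 visit. Then:

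pooled change from the designated baseline = pooled change from the first Study 002 visit + p × d

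Mean follow-up lengthens by p × L. With p assumed to be 13/52 = 0.25 to 39/52 = 0.75 ("Number of subjects: 52 completed") and L = 30 to 90 days, this runs from 0.25 × 30 = 7.5 days to 0.75 × 90 = 67.5 days.

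The shift in letters needs d. The document gives no value for d, nor its sign. The five-letter drop in the retreatment criteria is a trigger for one patient and says nothing about a group mean. The shift is zero if p or d is zero. Any figure in letters would be pure assumption, so none is offered.

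**4. Compare the passages.** Three points decide whether there is a contradiction.

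- The 12-month phrases in the Objectives set a limit, not a start date. The sentence about a whole year concerns safety during treatment. How long a patient is treated and which measurement serves as reference are separate choices, and both can stand together.
- Apart from vital signs, none of the items labelled with either study as source appears in Tables 1A and 1B. They are not measured again in the extension. A closing rule that says which earlier work-up stands in for a new one fits this well.
- If the rule does cover acuity and OCT, it is still determinate: each patient has one baseline, taken at entry to the earlier study.

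**The case for a change.** The strongest case for a change has four parts.

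- The rule is a separate bullet without limit, in a list that includes acuity and OCT. Calling the monthly measurements a repeat implies a first one, and no other baseline is named for them.
- Vital signs carry the either-study label yet are taken at every visit, so the label is not confined to one-time items.
- A SAP that followed the wording literally would inherit both starting points.
- A common origin looks available at no cost. Completing Study 002 is an inclusion criterion, and "Measurements and procedures at each visit will be the same as in protocol 002", so acuity and OCT at the first Study 002 visit probably exist.

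Part of this stands. The scope of the rule is not written down, and on the broad reading the two routes do have different spans. The rest does not carry a change. The protocol names no pooled estimate at Visit 13. Which value is the analysis baseline, how time is counted and whether results are shown by route are matters commonly left to a SAP, and none is at hand.

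The common origin also has a price. For Study 001 entrants, the first Study 002 visit may follow earlier study treatment; the document does not say. If it does, that reference is no longer pre-treatment, and any earlier effect drops out of the measured change. The present rule may exist to avoid this. Which origin is better depends on Studies 001 and 002, which cannot be seen here.

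Results by route would separate the spans but with less precision. With equal spread, the standard error relative to all 52 patients is √(52/n): 2.00, 1.41 and 1.15 for n = 13, 26 and 39.

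**Conclusion.** No change to the plan follows. The rule can give the two entry routes different baseline dates, but it does not contradict the objectives, which fix no start point. That their 12 months begin at Study 002 is an inference from the length of the extension and the visit numbers.

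On the narrow reading of the rule, acuity and OCT are untouched. On the broad reading, the span to the last visit is longer for Study 001 entrants by L. L, the share of such patients and their change before Study 002 are all absent from the document, so the effect on any average is unknown in size and sign and may be zero. The 7.5 to 67.5 days of extra mean follow-up rests wholly on assumed values.

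The unstated scope is a gap that an analyst fills when defining baseline, using the visit dates to show actual time since that measurement. Replacing the earliest baseline with a Study 002 origin would exchange one limitation for another, with no demonstrated gain.
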